TMS is a noninvasive method to cause depolarization or hyperpolarization in the neurons in the brain using electromagnetic induction to induce weak electric currents using a rapidly changing magnetic field. TMS is a novel intervention developed in the field of neurology that has been used in the treatment of patients suffering from migraine, stroke, Parkinson's disease, tinnitus and depression. In healthy subjects, high frequency rTMS over the left DLPFC has been shown to alter impulsive choice behavior (to decrease delay discounting) in healthy individuals and in smokers (12). On the other hand, a trial of TMS by one of the leaders in the field has shown it to be safe and well tolerated in recent suicide attempters suffering from depression with comorbid post-traumatic stress disorder and traumatic brain injury (13).

UAMS investigators have used repetitive transcranial magnetic stimulation (rTMS) to understand and treat phantom sound perception in subjects with tinnitus and to examine risky choices and impulsive behaviors using delay discounting in smokers. We propose to replicate a randomized controlled trial of rTMS over 3 days in a sample of well characterized acutely suicidal inpatients.

Our overall hypothesis is that 10 Hertz rTMS of the left dorsolateral prefrontal cortex (DLPFC) will correct impulsive choice behavior deficits found in acutely suicidal patients that in turn will translate into faster resolution of acute suicidal ideation. The current proposal will expand our understanding of the neurobiology of suicidal behavior by examining a potential neurocognitive mechanism of acute suicidality and test the value of rTMS as intervention for acute suicidal behavior. The current proposal will utilize behavioral assessments and rTMS in a randomized controlled trial in a group of adult patients hospitalized: a) following a recent suicide attempt with persistent suicidal ideation, or b) for severe suicidal ideation (n=20). To meet this goal we plan to recruit up to 28 individuals. Specifically, we propose:

The primary objective/endpoint of this study is safety. Adverse events will be collected throughout the duration of the trial. Any subject that meets the criteria for withdrawal (*Safety Assessments, page 14*) will be withdrawn from the study. The study will be stopped and all subjects withdrawn if two completed suicides by subjects receiving TMS occur during the active TMS treatment.

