Repetitive TMS (rTMS) will be delivered to the left PFC, defined as a location 6 cm (cm) anterior to the right hand motor thumb area. A research nurse will deliver the treatments. rTMS will be delivered with a figure-eight coil at 120% motor threshold, 10 Hertz (Hz), 5 s (s) train duration, 26 s intertrain interval for 50 min (6000 pulses) 3 times daily for 3 days (total 9 sessions, 54,000 stimuli). Similar parameters were previously used in a population of acutely suicidal veterans and military patients with even more severe comorbidity than our proposed sample because of comorbid posttraumatic stress disorder and traumatic brain injury without significant adverse effects (13). Variations will be allowed in the dosing schedule to accommodate the patient's inpatient schedule and staffing needs, with at least 1 hour between sessions. Treatments will be done on consecutive days, with the goal to deliver 9 sessions over three days. Adverse events will be assessed at each treatment session as well as daily. Prior to and then immediately after each rTMS session, subjects will complete visual analog scales (VAS) on a laptop computer located next to the rTMS chair. Patients will wear earplugs and will not be allowed to sleep. Counseling or other conversation during treatment will be discouraged.

Sham treatment

Parameters for sham rTMS are identical to those for active stimulation except that aluminum plate blocks the propagation of a magnetic field. The sound and physical sensation is the same as with the active coil while been biologically inactive.

Assessments

Trained and blinded study staff (raters) will administer assessments as described in Table 2. Additionally, menstrual cycle phase will be characterized for female subjects (i.e. date of last period, regularity of menstrual cycle).

PI: [name]

Table 2. Assessments administration schedule during the proposed study									
Task	Intake &	Pre rTMS	Post rTMS	Post	Before	3 & 6 month			
	Pre rTMS	Session 1	Session 3	rTMS	Discharge	follow-up			
	Session 1	(day 2 & 3)	(day 1 & 2)	Session 3					
	(day 1)			(day 3)					
Informed Consent Capacity	X								
Checklist									
Informed consent	X								
Demographic Data Form	X								
Columbia Suicide Severity Rating	X				X	X			
Scale (C- SSRS)									
Hamilton Rating Scale for	X			X	X	X			
Depression (HAM-D)									
Hamilton Anxiety Rating Scale	X			X	X	X			
(HAM-A)									
Beck Scale for Suicidal Ideation	X			X	X	X			
Beck Hopelessness Scale	X	X	X	X	X	X			

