The Principal Investigator will carefully monitor study procedures to protect the safety of research subjects, the quality of the data and the integrity of the study. To protect the identity of research volunteers, contact information will be stored in a separate file and locked cabinet, away from experimental data forms. All study subject material will be assigned a unique identifying code or number. The key to the code will be kept in a locked file in the Study Coordinator's office. Only [name] and designated research staff will have access to the code and information that identifies the subject in this study. All experimental data will be identified using a study code rather than a name, social security number, or other identifying information. All data collection forms will be kept in a locked cabinet in the Psychiatric Research Institute. Computer data records will remain on UAMS maintained password protected network drives.

DATA ANALYSIS

Cognitive tests and questionnaires

Data will be scored and analyzed/summarized according to instructions. Scores will be analyzed via t-tests, analysis of variance (ANOVA) or regression analysis.

PI: [name]

The primary outcome (impulsive choice measured by delay discounting) will be analyzed using an MMRM (mixed model repeated measures) approach based on a modified intent-to-treat (mITT) population. The mITT population will be defined as randomized subjects who started at least one treatment. Participants from the mITT population who are included in the MMRM model will also require both a baseline and at least one post- baseline SSI score. The model will include as the dependent variable change from baseline in delay discounting indifference point (K) at each post-baseline visit during the acute phase. Independent variables in the MMRM model will include treatment, visit, treatment-by-visit interaction, delay discounting at baseline, gender, age at baseline and diagnosis. Visits (Days 0, 1, 2, 3) will be treated as a categorical variable. Unstructured variance-covariance structure will be used. This same analysis will also be repeated on the completers' population, defined as subjects who completed 3 days of treatment with the scheduled maximum 6000 pulses per session.

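### The stated train timing and 50 min session do not give the stated 6,000 pulses, and no rule says which figure ends a session

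*Combined protocol and SAP*

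**What the plan says.** The section headed Active experimental treatment gives the frequency, train duration, interval, session length and pulse count in one sentence: "10 Hertz (Hz), 5 s (s) train duration, 26 s intertrain interval for 50 min (6000 pulses) 3 times daily for 3 days". The same sentence gives the course as nine sessions and 54,000 stimuli. Under Sham treatment, "Parameters for sham rTMS are identical to those for active stimulation", apart from the plate that blocks the field.

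The pulse count returns in Data Analysis. The primary model is repeated on completers, defined as "subjects who completed 3 days of treatment with the scheduled maximum 6000 pulses per session". The main analysis set has no such condition: "The mITT population will be defined as randomized subjects who started at least one treatment".

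The flexibility that the treatment section allows concerns how sessions are scheduled, with a minimum of one hour between them. Neither there nor elsewhere does the protocol say whether a session ends at 50 min or at 6,000 pulses. It also does not say whether the interval is counted from the end or the start of a train.

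**The concern.** Frequency, train length, interval and session length together determine the pulse count. A plan that states all five figures must therefore state a consistent set, and this one does not. Depending on which figure staff follow, the same text supports materially different exposures.

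Two things are at stake. First, Background and Rationale states that "The primary objective/endpoint of this study is safety". The safety results will be attributed to a stimulation regimen, and the number of pulses, or the time over which they are given, is part of that regimen. The risk section relies on these parameters too: it undertakes to follow published guidelines and argues that the regimen is milder than one used in an earlier trial. Neither statement can be fully checked while interval, session length and pulse count disagree.

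Second, the completers' definition uses the pulse count. If the stated timing and session length are followed, no session reaches that count.

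**Working it through.** **Inputs**, all from Active experimental treatment: 10 Hz; "5 s (s) train duration"; "26 s intertrain interval for 50 min"; 6,000 pulses per session; 9 sessions; 54,000 stimuli in total.

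**What reproduces.** 9 × 6,000 = 54,000. The per-session figure also matches the completers' definition. The pulse counts agree with each other, so the conflict lies between them and the timing.

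**Common quantities.** Pulses per train = 10 × 5 = 50. Session = 50 × 60 = 3,000 s. Trains needed for 6,000 pulses = 6,000 / 50 = 120.

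**Reading A: 26 s is the gap between trains** (the ordinary meaning of intertrain interval). Cycle = 5 + 26 = 31 s.
- 3,000 / 31 = 96.8 cycles, or 4,839 pulses pro rata.
- Complete cycles only: 96 × 50 = 4,800. The 97th train also fits (96 × 31 + 5 = 2,981 s), giving 97 × 50 = 4,850.
- Shortfall: 1,150 to 1,200 pulses, or 19.2% to 20.0% of 6,000.
- Nine sessions: 9 × 4,800 = 43,200 to 9 × 4,850 = 43,650, against 54,000.
- Time for 120 trains: 120 × 31 = 3,720 s = 62.0 min. Without the last gap, 119 × 31 + 5 = 3,694 s = 61.6 min.
- Excess over 50 min across nine sessions: 9 × 12 = 108 min, or about 104 min without the last gaps.

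**Reading B: 26 s runs from train onset to train onset** (most favourable to the plan). Cycle = 26 s.
- 3,000 / 26 = 115.4 cycles, or 5,769 pulses pro rata.
- Complete cycles only: 115 × 50 = 5,750. The 116th train also fits (115 × 26 + 5 = 2,995 s), giving 5,800.
- Shortfall: 200 to 250 pulses, or 3.3% to 4.2%.
- Nine sessions: 51,750 to 52,200, against 54,000.
- Time for 120 trains: 120 × 26 = 3,120 s = 52.0 min (51.65 min without the last gap).

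**Keeping both 6,000 pulses and 50 min.** Cycle = 3,000 / 120 = 25 s, so the gap is 25 − 5 = 20 s (20.2 s if no gap follows the last train), against a stated 26 s. Counted onset to onset, it is 25 s against 26 s.

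**Consequence for the completers' set**

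| Figures kept | Pulses per session | Figure that fails | Completers' definition |
|---|---|---|---|
| Timing and 50 min | At most 4,850 (A) or 5,800 (B) | 6,000 pulses | Nobody qualifies, in either arm |
| Timing and 6,000 pulses | 6,000 | 50 min (62 or 52 needed) | Works |
| 50 min and 6,000 pulses | 6,000 | 26 s interval | Works |

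**The case against.** The arithmetic is not in dispute, but several points can fairly be made about its size and effect.

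- **The size depends on an undefined term.** On the onset-to-onset reading the shortfall is about 2 min of a 50 min session, which could be rounding. This stands, and it is why both readings are given. That reading departs from the usual meaning, the protocol does not adopt it, and it still does not reach 6,000.
- **The pulse count looks like the intended target.** It appears per session, in the course total and again as a scheduled maximum in Data Analysis, all consistently. That makes a stop at 50 min with an empty completers' set the least supported of the three cases. But a population definition does not tell an operator when to stop.
- **Most of the regimen is fixed.** Intensity, frequency, train length, sessions per day and number of days are clear. What is open is how the interval and clock time fit the count.
- **The table is not exhaustive.** A 6.5 s train with a 26 s gap would also give 6,000 pulses in 50 min. This is correct as arithmetic, although the risk section repeats 5 s.
- **The analytic effect is limited.** The modified intent-to-treat analysis and the Fisher's exact comparison of adverse events use no pulse count, and the ambiguity is the same in both arms. This stands.
- **Detail may be in manuals, procedures or checklists.** It may, but those would not cure a contradiction within the protocol.
- **A separate end rule is redundant once the figures agree.** Not entirely: the risk section foresees pausing a session if the coil becomes warm, and after a pause elapsed time and pulse count diverge.

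**Conclusion.** The concern holds. No reading of the stated 10 Hz, 5 s, 26 s and 50 min gives 6,000 pulses. The shortfall is 19% to 20% per session if the interval is the gap between trains, and 3% to 4% if it is counted onset to onset. Equivalently, 6,000 pulses at the stated timing need about 62 min or about 52 min.

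The calculation assumes that the 50 min is all stimulation time. Any set-up within it would make the shortfall larger. The empty completers' set is conditional on sessions ending at 50 min with the stated timing and on the definition being applied literally.

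This should be corrected because the exposure figures underlie a trial whose primary objective is safety and also define an analysis population. It introduces no difference between arms and does not affect the main analysis set. Nothing here says which stimulation figure is right.

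**What to change.** Under Active experimental treatment, the sponsor should reconcile train duration, interval, session length, pulses per session and course total so that they agree arithmetically, and define whether the interval runs from the end or the onset of a train. The same section should state whether elapsed time or pulse count ends a session, including after a pause. The completers' definition in Data Analysis should then be worded to match that rule, and the sham section will follow because it takes the same parameters. Which values to adopt is for the sponsor and investigators.

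The cost is amendment wording, with no new data or patients.

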Visual Analog Scale	Approx. 10 min	A custom developed Visual Analog Scale (VAS) questionnaire will be administered on a laptop computer pre and post each treatment session. Subjects are asked to rate their treatment experiences using the following descriptors: happy, irritable, angry, excited, confused, calm, sad, anxious, nervous, bored, relaxed, tired, distracted, discomfort, and suicidality (13) VAS scores are converted to a scaling of 0-99 points.		
Sham validating measure	Approx. 2 min	Subjects are asked two questions regarding their perception of receiving treatment or placebo.		
MINI International Neuropsychiatric Interview (MINI)	Approx. 30 min	Structured clinical interview for DSM-IV and ICD-10 psychiatric diagnoses. It is fully validated and is a more time-efficient alternative to the SCID.		
Young Mania Rating Scale	Approx. 10 min	Used to assess manic symptoms. The scale has 11 items and is based on the patient's subjective report of his or her clinical condition over the previous 48 hours.		
Delis-Kaplan Executive Function System (DKEFS) Verbal	Approx. 3 min	A verbal fluency test that measures spontaneous production of words belonging to the same category or beginning with some designated letter.		

C-SSSRS, HAM-D, HAM-A, MINI and other rating scales will be administered by a trained member of the research team.

Randomization

A predefined, computer-generated randomization sequence will assign participants in a 1:1 ratio to active vs. sham rTMS groups using a block size of 6. This sequence assignment will occur prior to the initiation of the study. Following completion of baseline assessments each subject will be assigned a sealed envelope with X or Y which will stand for active or sham stimulation.

The blind will be broken following completion of data gathering and analysis.

TMS

A NeuroStar TMS Therapy System and NeuroStar XPLOR Clinical Research System coil system (Neuronetics, Malvern Pennsylvania) will be used to deliver stimulation. The manuals for the stimulator and

PI: [name]

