Delay discounting task	X	X	X	X	X	X			
N back test	X	X	X	X	X	X			
Stroop Test	X	X	X	X	X	X			
Young Mania Rating Scale	X	X	X	X	X	X			
DKEFS Verbal Fluency Test	X	X	X	X	X	X			
Pressure pain threshold	X	X	X	X	X	X			
Sham validating measure				X					
Trail making A and B	X	X	X	X	X	X			
Visual Analog Scales**	X	X	X	X	X	X			
MINI International	X								
Neuropsychiatric Interview (MINI)									
Randomization	X								

^{**} This assessment will be collected 3 times per day pre and post rTMS.

Safety Assessments

Research staff will use the MedDRA System Organ Class (SOC) and preferred term (PT) to document adverse events, which will be assessed at each treatment, and at follow-up visits.

This protocol will not modify patient care and our visits will not interfere with regular clinical care, except in the case of imminent danger to the patient or others in which appropriate measures will be taken, like contacting the primary treatment team and placing the patient on 1:1 observation until evaluation by the primary team.

STUDY POPULATION

Participant recruitment will occur at the inpatient units at the Psychiatric Research Institute (PRI). Target sample size is 20, which will be randomized into active or sham groups (1:1). Considering 40% attrition rate we plan to recruit 28 participants.

Recruitment: Recruitment will be facilitated by the PI's role of PRI inpatient attending physician. The success of this proposal depends heavily on the ability to recruit patients very soon after hospitalization for

PI: [name]

suicide ideation or behavior.

All participants will be compensated \$40 for their participation in each of the 3 rTMS sessions of the active phase of the study and the 2 follow-up sessions. Participants can earn a total of \$200 for completing the entire study, including both follow up visits.

Inclusion Criteria

- a) Age 18-60 years, of all races and ethnicities;
- b) Admitted voluntarily to the adult psychiatric inpatient at PRI;
- c) Suffering from a current depressive episode as defined by the DSM-V
- d) Currently have diagnoses of major depressive disorder
- e) Reason for hospitalization should be a recent suicide attempt or suicidal ideation
- f) Current severe suicidal ideation defined by a score >7 in the Beck Scale for Suicidal Ideation
- g) Must pass the TMS safety checklist (TASS)
- h) Women of childbearing age must have a negative result on a pregnancy test
- i) Ability to read, write and speak English.

Exclusion Criteria

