Analyses of VAS data will be conducted using a similar MMRM approach. Each VAS item will be analyzed separately. For the suicide, mood and anxiety items, the model included as the dependent variable change scores from pre-session 1 (session prior to intervention) to each post-session (sessions 1-9) during the acute phase. Independent variables included treatment, session, treatment-by-session interaction, VAS score at pre-session 1, gender, age at baseline, and diagnosis. Painfulness questions collected only at each post-session will be analyzed using an MMRM approach with post-session scores as the dependent variable. Independent variables will remain the same.

Descriptive analyses will be performed to compare baseline data between treatment groups. Categorical variables will be evaluated using Fisher's exact test. Continuous variables will be analyzed with Wilcoxon's rank sum test.

Safety data will be summarized overall and by treatment groups. Fisher's exact test will be used to compare the number of subjects between groups who experienced any adverse events. Length of hospital stay will be compared using Wilcoxon Rank Sum test. Time to re-admission will be analyzed with log-rank test.

The Stroop Test, N-Back scores and pain pressure threshold will be added as covariates in final analysis. Other secondary efficacy outcomes (HRSD, MADRS, CAPS and SSI) for the extended safety phase will be analyzed with MMRM model. The model will include the change from baseline at each follow-up visit as the dependent variable. Independent variables include treatment, visit, treatment-by-visit interaction and base- line score.

We will use repeated measures ANOVA (with appropriate statistical corrections) to compare measures obtained at baseline to those collected 3 & 6 months after all experimental treatment ends. This analysis will address long-term effects of rTMS experimental treatment on suicidal ideation.

The integrity of the blind will be analyzed by tables and Fisher's exact test.

All statistical analyses will be performed in R version 2.14.0. Because this is an early phase study, no adjustments will be made for multiple comparisons, and a *P*-value of 0.05 will be considered to be statistically significant.

Power estimation

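### Raters may learn the patient's guess of active or sham before later HAM-D, HAM-A and C-SSRS ratings, because the plan gives them the sham validating measure and does not shield them from the answers

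*Combined protocol and SAP*

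**What the plan says.** Under Study Design and Procedures, the Assessments section assigns the work in one sentence: "Trained and blinded study staff (raters) will administer assessments as described in Table 2". It makes no exception for any row.

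Table 2 contains a row for the "Sham validating measure", with a single mark in the column for the end of session 3 on day 3. Table 1 describes it: "Subjects are asked two questions regarding their perception of receiving treatment or placebo". It does not say whether the answers are given aloud, on paper or on a computer.

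A note under Table 1 adds: "C-SSSRS, HAM-D, HAM-A, MINI and other rating scales will be administered by a trained member of the research team". It names no separate person to collect the guess.

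The Randomization section keeps the blind in place until data collection and analysis are finished, so ratings at discharge and at 3 and 6 months are meant to be blinded. In Data Analysis, the later ratings feed this plan: "Other secondary efficacy outcomes (HRSD, MADRS, CAPS and SSI) for the extended safety phase will be analyzed with MMRM model". The same section says the integrity of the blind will be examined with tables and Fisher's exact test. It does not say who may see the answers before then.

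**The concern.** Asking patients for their guess is a sound check of the blind. The difficulty is the route. The people told to administer the check are also the outcome assessors, and they still have scales to score afterwards. A rater who knows that a patient believes the stimulation was real, or believes it was sham, may score an interview-based scale a little differently.

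If guesses are distributed differently in the two arms, that tendency becomes a between-arm bias in the clinician-rated results. With a target of 20 patients randomised 1:1, and no guess collected from the raters themselves, such a bias would be hard to detect afterwards.

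**Working it through.** The plan gives no figure to reproduce. The check sets the staffing statement against the Table 2 schedule and counts the ratings that come after the guess.

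**Step 1. Who collects the guess.** The Assessments section gives the Table 2 assessments to the raters, and the sham validating measure is a Table 2 row. Where Table 1 intends self-completion, it tends to say so: the Beck Scale for Suicidal Ideation is called self-report, and the VAS is given on a laptop. The sham measure carries no such wording. No section gives it to someone else, seals the answers, or places it after that visit's ratings.

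**Step 2. What follows the guess.** Post-baseline time points in Table 2, counting months 3 and 6 separately:

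| Scale | Before the guess | Same day 3 point, order not fixed | After the guess | Total |
|---|---|---|---|---|
| HAM-D | 0 | 1 | 3 (discharge, months 3 and 6) | 4 |
| HAM-A | 0 | 1 | 3 | 4 |
| C-SSRS | 0 | 0 | 3 | 3 |
| YMRS | 4 (pre-session on days 2 and 3; post-session on days 1 and 2) | 1 | 3 | 8 |

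So 3 of 4 HAM-D and HAM-A time points and 3 of 3 C-SSRS time points come after the guess. The remaining HAM-D and HAM-A time point falls in the same column as the guess, and nothing fixes which comes first.

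**Step 3. Which analyses use those ratings.** The extended-phase model takes change from baseline at each follow-up visit. Reading HRSD as the HAM-D of Table 2, every response in that model is rated after the guess. The C-SSRS has no named model or test in Data Analysis. The delay discounting model covers Days 0 to 3 and uses a choice task. The Beck scale is completed by the patient.

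**Step 4. Form of the bias.** If raters know the guess and score patients who believe they had active treatment lower by *s* points, then

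bias = *s* × [P(guesses active | active arm) − P(guesses active | sham arm)].

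It is zero if *s* = 0 or if the two probabilities are equal. The documents give neither input. Purely as assumptions, with *s* from 1 to 3 HAM-D points:

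- guess rates of 80% and 40%: 1 × 0.4 = 0.4 to 3 × 0.4 = 1.2 points;
- guess rates of 70% and 50%: 1 × 0.2 = 0.2 to 3 × 0.2 = 0.6 points.

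These also suppose that every later rating is made by someone who knows the guess. They show how the mechanism works and are not an estimate for this trial.

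**The case against.** A reader might infer that the raters are certain to hear each guess and are in effect unblinded for everything that follows. The documents do not support that.

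- **Mode and person.** The text does not say that the answers are spoken or that one rater follows a patient throughout. Raters are mentioned in the plural. Patients complete the VAS themselves although it is a Table 2 row, so administering a row could mean handing over a form whose answers the rater never reads.
- **Scope.** Table 2 also lists consent, the demographic form and randomisation, so the staffing sentence is a general one and should not be pressed too literally.
- **Guess versus allocation.** A guess does not reveal the assignment. The coils are unmarked and look alike, and the protocol states that sham sounds and feels the same as active. If that holds, guesses should not differ by arm and the bias vanishes.
- **Importance.** Safety is the primary objective, delay discounting is the outcome called primary in Data Analysis, and the suicidal ideation hypothesis uses a self-report scale. HRSD is a secondary outcome in a pilot, and the C-SSRS is tied to no specified comparison.

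All of this stands. It limits the point to a possible exposure of the rater group and leaves its size unknown. It does not remove the gap: staff who follow the stated rule can learn the guess, and nothing in the plan prevents it. The sham is designed to equalise guesses, but the plan rightly tests this instead of assuming it. The Risks section lists scalp-muscle twitching as a likely effect of stimulation, which gives patients something to guess from.

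**Conclusion.** The point holds as an avoidable risk of rater expectation bias. The plan assigns the sham validating measure to the raters and does not shield them from the answers. As a result they may know a patient's guess at the three later HAM-D, HAM-A, C-SSRS and YMRS time points, and possibly at the day 3 HAM-D, HAM-A and YMRS.

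The counts come directly from Table 2. The size of any bias cannot be derived from the documents: it depends on whether raters see the answers, whether they are influenced, and whether guesses differ by arm. If any of these fails, the bias is zero.

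The exposed results are secondary and safety scales, chiefly the extended-phase HRSD analysis. It would be wrong to conclude that the delay discounting result or the self-report Beck scale is compromised. The change is worth making because it is cheap and removes the route altogether.

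**What to change.** In the Assessments section, except the sham validating measure from the rater-administered assessments, and state that:

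1. the patient completes the two questions alone on the laptop already used for the VAS, once the day 3 ratings are finished, as a separate short form and not as part of the last post-session VAS;
2. the answers are kept from the raters until the last 6-month rating is complete;
3. patients are asked not to discuss their guess with raters.

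The measure stays in its present Table 2 column, and the Fisher's exact analysis of the blind is unchanged.

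The cost is minor questionnaire set-up, restricted access to two data items until follow-up ends, and a short instruction to patients. No extra staff, visits or patients are needed. If raters are already kept away from the guess in practice, the change only records that.

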Based on our previous results, we consider a meaningful clinical difference as one equal to or higher than that found between recent suicide attempters with persistent suicidal ideation (delay discounting rate (K)=0.122) compared to depressed patients with active suicidal ideation (K=0.099), thus d=0.23 (1).

Given these effect sizes, we determined that a sample of 10 experimental treatment responders will yield power of .80 or greater to detect change in tinnitus. We expect that the sample size proposed for this pilot study, 20 subjects, is sufficient to test our hypothesis as planned.

PI: [name]

ETHICAL CONSIDERATIONS

This study will be conducted in accordance with all applicable government regulations and University of Arkansas for Medical Sciences research policies and procedures. This protocol and any amendments will be submitted and approved by the UAMS Institutional Review Board (IRB) to conduct the study. Given the transient state (severe acute suicidal ideation) targeted in this study, the earliest assessment of these patients is crucial in order to obtain a glimpse of the state of mind of the individual that led to engage in suicidal behavior or to ask for help in order to prevent doing so.

Vulnerable population: An ethical concern is that some patients may be receiving medical care involuntarily, and thus represent a vulnerable population with compromised ability to provide informed consent. Thus, no involuntary patients will be recruited in this study. We have ongoing projects [UAMS IRB#139056] and have executed successfully previously similar studies [University of Miami IRB# 20110619] with acutely suicidal patients in collaboration with IRB panels. Additionally, even though these patients have recently attempted suicide or are acutely suicidal, the fact that they would be hospitalized provides an additional layer of protection to this vulnerable population. We will work closely with the IRB to assure that all ethical concerns are addressed.

STUDY REGISTRATION AND PUBLICATION

The PI, Co-Is, and associates are active researchers and publish in a variety of academic journals. It is anticipated that results from this study will be published in similar academic journals. All manuscripts published in peer-reviewed journals will be made publicly available in PubMed Central as per the requirements for studies supported by NIH funding.

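### Recruiting 28 does not protect a target of 20 at the stated 40% attrition: about 17 would be expected to remain, and 28 covers a loss of at most 28.6%

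*Combined protocol and SAP*

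**What the plan says.** The Study Population section of the combined protocol and SAP gives the target as "Target sample size is 20, which will be randomized into active or sham groups (1:1"). The next sentence reads "Considering 40% attrition rate we plan to recruit 28 participants".

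The Background and Rationale section repeats the target of 20 and adds "To meet this goal we plan to recruit up to 28 individuals", so 28 is a ceiling there. The Power estimation section relies on the same target, stating that "the sample size proposed for this pilot study, 20 subjects, is sufficient to test our hypothesis as planned".

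Two definitions in the Data Analysis section bear on who would be affected by losses. The modified intent-to-treat set is described as follows: "The mITT population will be defined as randomized subjects who started at least one treatment". The completers' set consists of "subjects who completed 3 days of treatment with the scheduled maximum 6000 pulses per session".

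The document gives no formula linking 20, 40% and 28, no rule for replacing participants who leave, no second attrition rate, and no statement of whether attrition is counted before randomization, during the three treatment days, or by the 3- and 6-month visits.

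**The concern.** An attrition rate applies to the people recruited, so 40% attrition should leave 60% of 28. That is clearly fewer than the 20 the plan says it needs, and with 28 as a ceiling the text offers no way to make up the difference.

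What is at stake depends on when people leave:

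- **Before randomization.** About 17 would be randomized, although the Study Population section says 20 will be.
- **During the three treatment days.** The completers' set shrinks. The main delay-discounting model may shrink too, because the Data Analysis section admits to it only participants with a baseline and at least one post-baseline SSI score. If SSI means the Beck Scale for Suicidal Ideation, Table 2 first schedules it after baseline following the last session on day 3.
- **By 3 or 6 months.** The follow-up analyses lose participants, while the acute-phase analysis may keep them.

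**Working it through.** **Inputs**

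- Target: 20, allocated 1:1, so 10 per arm (Study Population; also Background and Rationale and Power estimation).
- Attrition: 40% (Study Population).
- Recruits: 28 (Study Population; a maximum of 28 in Background and Rationale).

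**Step 1: reproduce the plan's figure.** Target × (1 + rate) = 20 × 1.40 = 28. This matches exactly, but it adds 40% of the target. It does not allow for losing 40% of the recruits.

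**Step 2: apply the stated attrition to 28.** Expected losses are 28 × 0.40 = 11.2. Expected remaining are 28 × 0.60 = 16.8, or 8.4 per arm. The shortfall is 20 − 16.8 = 3.2, and 3.2 / 20 = 16%.

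**Step 3: the largest loss that 28 can absorb.** (28 − 20) / 28 = 8 / 28 = 28.6%.

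**Step 4: recruits needed if both 20 and 40% are kept.** Target / (1 − rate) = 20 / 0.60 = 33.3, rounded up to 34. The plan's figure is 6 below this.

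**Step 5: how the result moves with the rate.** Expected remaining = 28 × (1 − rate).

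| Attrition | Expected remaining of 28 |
|---|---|
| 20% | 22.4 |
| 25% | 21.0 |
| 28.6% | 20.0 |
| 30% | 19.6 |
| 40% | 16.8 |

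**Step 6: chance of reaching 20.** Assume each recruit stays with probability 0.60, independently of the others. The number remaining is then Binomial(28, 0.60), with median 17 and P(at least 20) = 0.148. The target would be missed about 85% of the time.

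**Step 7: effect on precision, for illustration only.** This uses an unadjusted two-sample t-test with two-sided alpha 0.05, not the planned mixed model.

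| Per arm | Detectable d at 80% power | Power at d = 0.23 |
|---|---|---|
| 10 + 10 | 1.32 | 7.8% |
| 9 + 9 | 1.41 | 7.4% |
| 9 + 8 | 1.46 | 7.3% |
| 8 + 8 | 1.51 | 7.1% |

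The value d = 0.23 is the difference that the Power estimation section calls clinically meaningful. On this test, power for it is very low at every size shown, so the attrition error is not what limits power. Whether 20 is adequate is a separate matter.

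**The case against.** The strongest reply is that 40% was never meant as a loss rate. Since 20 × 1.40 is exactly 28, it may be an over-recruitment margin under the wrong name, and the error would then be one of wording with no effect on design or analysis. This is plausible, and it is the only reading under which all three figures agree. But the text says attrition, and a reader who plans on a 40% loss would be misled. The sentence needs correcting on this reading too.

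A second reply is that the consequence is small. The study is described as a pilot, its stated primary objective is safety, and against the protocol's own effect size the fall from 20 to about 17 hardly changes power (step 7). That stands, and it is why the point should not be presented as a loss of power. It does not make the figures agree.

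A third reply is that the modified intent-to-treat analysis keeps people who leave early. This holds for those lost after the acute phase. It is less secure for those lost during treatment, because of the SSI condition described above. It does not help if the loss comes before randomization.

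Reading attrition as loss before randomization does not rescue the figure either, because 40% of 28 lost still leaves about 17 to randomize.

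**Conclusion.** The inconsistency is real and can be verified from two adjacent sentences. At the stated 40% attrition, 28 recruits are expected to leave 16.8 participants against a target of 20, a shortfall of 16%. The target is met only if at most 8 of 28 are lost.

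These results use only the plan's own figures. The 15% chance of reaching 20 also assumes independent losses at exactly 40%. Which analysis bears the shortfall cannot be determined, because the stage of attrition is undefined.

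The sponsor should correct this. A core design figure is wrong as written, although the practical effect may be modest.

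**What to change.** Rewrite the attrition sentence in the Study Population section. Say at which stage attrition is counted: before randomization, during the three treatment days, or by the 3- or 6-month visit. Then use whichever of these wordings reflects what was meant:

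1. If 40% is the loss actually expected, state that 28 recruits are expected to leave about 17 participants, 8 to 9 per arm.
2. If a lower loss can be justified, state that 28 allows for about 29% attrition (8 of 28), and give the basis for that rate.
3. If 40% was a margin, state that recruitment is set 40% above the target of 20, and do not call it attrition.

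Wording 1 also requires the figure of 20 to be revised in the Background and Rationale and Power estimation sections. Wordings 2 and 3 leave 20 and 28 as they are, so those sections need no edit.

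The cost is one sentence, plus matching figures under wording 1, and no added enrolment. The price is that the expected sample or the attrition allowance looks less favourable than it does now. Keeping both 20 and 40% would mean recruiting 34. That is a larger decision and is not needed to make the text correct.
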